RESEARCH PROTOCOL

Date	December 27, 2022
Title	Evaluating the use of pre-epidural placement of SCDs to prevent
	hypotension
Principal Investigator	[name], MSN, RN, APRN, FNP-C
Sub-Investigators	[name], MSN, RNC-OB, C-EFM; [name], MSN, RNC-
	OB, C-EFM; [name], BSN, RNC-OB, C-EFM; [name], BSN, RNC-OB, C-EFM
Research Specialist	[name], RN, CPN
Department	Bethesda North Hospital, Labor & Delivery
Hatton #	21-020

Purpose of Study

Women given epidural analgesic during labor often experience hypotension. When this happens, it typically occurs in the first 30-60 minutes after epidural placement. This maternal low blood pressure can result in decrease perfusion of the placenta and ultimately impact blood flow to the infant which is seen through decreases in the infant's heart rate.

Hypothesis or Research Question

- Hypothesis 1: Laboring women who receive epidural analgesia and use sequential compression devices (SCDs) will experience a lower incidence of hypotension compared to laboring women who receive epidural analgesia and do not use SCDs.
 - *hypotension is defined as SBP < 90 mmHg or an SBP decreases more than 20% from baseline
- Hypothesis 2: Infants of laboring women who receive epidural analgesia and use SCDs will experience a lower incidence of Category 2 tracings compared to laboring women who receive epidural analgesia and do not use SCDs.

Background

Women given epidural analgesic during labor can experience hypotension. Hypotension is defined as a systolic blood pressure of less than 90 mm Hg or diastolic blood pressure of less than 60 mm Hg. Maternal physiologic changes such as increased blood volume will have an impact on the circulation system; low maternal blood pressure can result in decreased perfusion of the placenta and ultimately impact blood flow to the fetus, which is seen via a category II or III fetal heart rate monitoring. While hypotension may not cause problems for some non-pregnant women, the fetus in utero is used to and dependent on a certain blood pressure threshold.

When hypotension related to epidural placement, this can occur within 15-60 minutes after placement. The purpose of this study is to build upon this preliminary work and to use a randomized controlled trial to examine the effectiveness of SCDs in preventing hypotension among a larger sample of laboring women who receive an epidural analgesia.

Lower limbs venous compression has been demonstrated to effectively decrease hypotension among women undergoing scheduled cesarean section (Cyna, Andrew, Emmett, Middleton, & Simmons, 2006; Goudie, Winter, & Ferguson,, 1988; Rout, Rocke, & Gouws, 1993; Sun et al., 2004; Van Bogaert, 1998). To date, only one study has examined the use of lower limbs venous compression to decrease hypotension in laboring women and found a significant reduction in maternal hypotension with the use of SCDs. This study compared women who used SCDs to a historical comparison group of women who received care before SCDs were provided and found a decrease in the incidence of maternal hypotension from 23.3% in the comparison group to 3.23% in the SCD group. and the researchers suggest a prospective randomized trial to investigate the phenomenon (Peyronnet et al., 2017). The purpose of this study is to build upon this preliminary work and to use a randomized controlled trial to examine the effectiveness of SCDs in preventing hypotension among a larger sample of laboring women who receive an epidural analgesia.

Research Plan

• Study Design

- This study will use a randomized, non-blinded, controlled design with two arms:
 - Arm 1: Patient will receive 1L of LR and have SCDs applied 15 minutes before epidural placement and will be removed 1 hour after epidural placement
 - Arm 2: Patient will receive 1L of LR during and after epidural placement with no use of SCDs

• Setting for the study

The study will take place on Bethesda North Hospital's Labor and Delivery Unit. This unit houses 12 labor rooms and provides care to approximately 10-12 laboring women each day.

• Participants

The study will enroll 120 women who meet the following inclusion/exclusion criteria:

Inclusion Criteria:

- \circ $\;$ Laboring at Bethesda North Hospital Labor & Delivery Unit
- Will receive epidural analgesia
- 37+ weeks gestation
- Singleton pregnancy
- Category 1 tracings only before epidural placement

Exclusion Criteria:

- Under 18 years old
- Does not speak English
- o Unable to consent to involvement in the research study
- Diagnosed with fetal demise
- Diagnosis of pre-existing hypertension
- Diagnosis of gestational hypertension

- Diagnosis of pre-eclampsia
- Diagnosis of diabetes
- Breech presentation
- Contraindications to lower leg compression (ex: fractured bones in leg, cellulitis, lower limb amputation, etc.)
- Contraindications to receiving 1L of LR
- Blood pressure on admission SBP>160 or DBP>110
- Fetal heart rate abnormalities before epidural

Sample Size Determination: A power analysis was conducted using the primary outcome variable, maternal hypotension, with an expected difference similar to that found in the Peyronnet and colleagues' (2017) study (3.23% vs. 23.3%) (0.3), power of 0.8, and level of significance 0.05. It was determined that 44 patients would be needed in each group, for a total sample size of 88 patients. To allow us to also examine the impact on occurrence of infant Category 2 tracings and to allow for the possibility of removing participants from the final analysis due to missing data, we plan to enroll 120 patients (60 in each group).

• Data Collection

Before the study begins, information about the study will be provided to the providers. Providers who agree with involvement of their patients will be provided a hand-out about the study to give to their patients during prenatal visits and asked to mention to their patients that they may be approached about involvement of the study when they are admitted. The nurses on the L&D unit will be provided with education about the study purpose, exclusion criteria, and procedures. All nurses on the L&D unit have received training in the proper use of SCDs clinically. However, to validate and reinforce this knowledge, the nurses on the L&D unit will be provided education on proper measurement to determine boot size for SCDs and proper boot placement and SCD use. Nurses will be instructed to call a member of the study team immediately if any safety concerns occur related to the SCDs.

When a patient who meets the inclusion/exclusion criteria is admitted, a nurse will describe the study, answer any questions the patient has, and if the patient wants to enroll in the study, the study team nurse will review the information consent form. After the patient provides written informed consent, the nurse will remove the next envelope out of a box of prefilled and sealed opaque envelopes. The envelope will provide the Subject ID number to be used on all study-related documentation and the study Arm that the patient has been randomized to, either:

- 1. SCD Group + Fluid Bolus
- 2. Fluid Bolus Group (no SCD)

These envelopes will be filled using a computerized simple random number generator (1:1 randomization) prior to the start of the study.

In addition to the group assignment, the envelope will include a data collection form. Data will be recorded directly on this form during the patient's visit. The form will collect the following information:

- \circ Whether patient was assigned to the SCD group or the standard care group
- Patient demographics including age, weight, and # pregnancies and # births
- Threshold systolic blood pressure (20% decrease from baseline) The study team nurse will calculate threshold systolic blood pressure by calculating the admission systolic blood pressure multiplied by 0.8
- \circ Biomed number of SCD machine (SCD group only)
- Leg measurement for SCD boot size determination (SCD group only)
- Size of boots placed (SCD group only)
- Biomed number of boots placed (SCD group only)
- Time SCDs placed on (SCD group only)
- o Time of epidural placement
- Whether patient received 1L of LR
- Time SCDs removed (SCD group only)
- Did the RN have to perform any interventions to address decreased fetal heart rate during the 1 hour after epidural placement? Yes/No
- Did the anesthesia provider treat the maternal blood pressure during the 1 hour after epidural placement? Yes/No
- All BPs and times of maternal blood pressures with SBP<90 or >20% decrease from baseline within the 1 hour after epidural placement

After delivery, the RN will complete the data collection form and place the signed informed consent form and data collection form in a locked room designated for study materials.

On the data collection forms, RNs are instructed to call a member of the study team immediately if there are any safety concerns related to the SCDs. If the study team receives a call about a safety concern, recruitment and enrollment of new participants will stop until the study team meets and reviews the incident and determines it is safe to continue. Any adverse events and serious adverse events will be reported to the IRB in compliance with IRB safety policies.

Weekly, the research specialist will collect the data collection forms. The research specialist will review the data collection forms and compile the medical record numbers for any patient who the RN marked "yes" to "Did the RN have to perform any interventions to address decreased fetal heart rate?" The research specialist will send two study team nurses the compiled list for the week to conduct a review of the medical records of the patients requiring interventions to address decreased fetal heart rate. The same two study team nurses will review all charts throughout the study and they will separately determine category of the fetal heart tracings and send them to the research specialist. The two study team nurses assigned to determine tracing categories will be blinded to which group the patient was in. The

research specialist will conduct interrater reliability each week and any discrepancies will be sent back to the two raters to review together and come to a consensus on category assignment.

• Intervention or experimental aspect of the study

Patients randomized to Arm 1 will have SCDs placed on their lower limbs 15 minutes before the epidural placement and they will be removed one hour after epidural placement. SCD use is in the Epic order set for laboring patients but is rarely used in practice on the unit. The SCD in clinical use at Bethesda North Hospital is the Kendall SCD Express Sleeves, knee length 700 series, Ref: 29525. In this study, the study team is using the device according to the indicated description "as the sleeves/cuffs compress the legs/feet, veins collapse, forcing the blood to move upward towards the heart" but not for the indicated outcome of "prevention of DVTs"; instead the study is testing the use of this device for a new indication – for prevention of maternal hypotension.

Patients randomized to Arm 2 will receive standard care.

• Statistical Analysis

Data recorded on paper data collection forms will be entered into a password protected database. Only study team members will have access to the database. No personal information will be entered into the electronic database. Data will undergo range checks when entered into the database, and quality control procedures will be performed to ensure accuracy of the data in the electronic database.

Statistical analyses will be performed using Intellectus Statistics statistical software. The following analyses will be performed to address each hypothesis:

Hypothesis 1: Laboring women who receive epidural analgesia and use SCDs will experience a lower incidence of hypotension compared to laboring women who receive epidural analgesia and do not use SCDs.

To compare the effects of the SCDs, a Chi Square test will be used to compare occurrence of maternal hypotension for patients who used SCDs to patients who did not use SCDs. A level of significance of α =0.05 will be used.

Hypothesis 2: Infants of laboring women who receive epidural analgesia and use SCDs will experience a lower incidence of Category 2 tracings compared to laboring women who receive epidural analgesia and do not use SCDs.

To compare the effects of the SCDs, a Chi Square test will be used to compare occurrence of Category 2 tracings of infants of patients who used SCDs to infants of patients who did not use SCDs. A level of significance of α =0.05 will be used.

Interim data analysis will occur (1) once approximately 1/3 of the participants have been enrolled in each group and (2) once approximately 2/3 of the participants have been

enrolled in each group. If interim calculations at time (1) or time (2) note a significant difference between groups in maternal hypotension or frequency of category 2 tracings, data collection will be completed at that time and final analysis will be completed.

Ethical Considerations

• Informed consent

All study staff will complete CITI training. A study staff member will meet with potentially eligible patients and describe the study and answer any questions. If the patient is interested and meets all the inclusion/exclusion criteria, the study staff will review the *Informed Consent Form* and obtain written informed consent. Patients will receive a copy of their signed Informed Consent form.

Informed Consent forms will be stored in a locked room that only staff will have access to. After the study closes, the signed Informed Consent forms will be boxed and sent to off-site storage and securely stored until the infant turns 21 years of age. At that time, the hard copy forms will be shredded.

• Privacy information

Personal identifiers will not be entered into the electronic database. Hard copy data collection forms and Informed Consent forms will be stored in a locked room that only staff will have access to. Electronic data will be stored on a password-protected folder on the U drive. Only study staff will have access to the electronic study documents. After data analysis and dissemination is completed, hard copy forms will be boxed and sent to off-site storage and securely stored until the infant turns 21 years of age. At that time, the hard copy forms will be shredded.

Cost/Budget

There will be no costs to conduct this study and no additional charges to patients.

Estimated Period of Time to Complete Study		
When will study begin?	2.25.2021	
Protocol Development	1 week	
Completed		
Admin Review Time	2 weeks	
IRB Approval	6 weeks	
Data collection	3 months	
Data analysis	1 month	
Presentation development	2 weeks	
(if applicable)		
Manuscript Development	1 month	
(if applicable)		
Journal submission process	3 months	

(if applicable)	
Study closure	1 week

• When and how will results be disseminated?

Results will be disseminated internally to the TriHealth perinatal leadership team and system-wide through the TriHealth Research Council. Results will be disseminated nationally through presentation at a professional organization conference. Finally, results will be disseminated nationally and internationally by publication in a relevant peer-reviewed journal.

References

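### The timing of the 1 L fluid bolus is stated for Arm 2, unclear for Arm 1 and not recorded; if it differs by arm, the SCD effect is confounded with fluid timing

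*Combined protocol and SAP*

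**What the plan says.** Fluid timing appears in one place only, the two arm definitions under Research Plan, Study Design:

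- Intervention arm: "Arm 1: Patient will receive 1L of LR and have SCDs applied 15 minutes before epidural placement". The sentence goes on to say that removal is one hour after the epidural.
- Control arm: "Arm 2: Patient will receive 1L of LR during and after epidural placement with no use of SCDs".

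The other relevant text is silent on when the fluid is given:

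- **Data Collection, envelope labels.** Both arms are labelled as receiving a fluid bolus, one with SCDs and one without. No timing is given.
- **Data Collection, form items.** The form takes the time of the epidural, the times the SCDs go on and come off, and the times of qualifying low blood pressures. For fluid it takes only "Whether patient received 1L of LR".
- **Data Collection, chart review.** Two study nurses are to "conduct a review of the medical records of the patients requiring interventions to address decreased fetal heart rate", and their task is to rate the fetal tracings.
- **Intervention or experimental aspect of the study.** For the SCD arm, this section reads "Patients randomized to Arm 1 will have SCDs placed on their lower limbs 15 minutes before the epidural placement", with no mention of fluid. For the other arm: "Patients randomized to Arm 2 will receive standard care".
- **Statistical Analysis, Hypothesis 1.** An unadjusted chi-square test of hypotension by SCD use at α = 0.05.

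On blinding, the Study Design section says: "This study will use a randomized, non-blinded, controlled design with two arms".

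**The concern.** Hypothesis 1 attributes any reduction in hypotension to the SCDs, so the arms should differ in SCD use and nothing else that might affect blood pressure in the first hour. The fluid is part of both regimens, and women who cannot safely receive it are excluded. A nurse who follows the two arm definitions literally could give Arm 1 the litre before the epidural and Arm 2 the litre during and after it.

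The arms would then differ in two respects. Randomization would not remove the second difference, because it would be part of the assigned regimen. Because treatment is open, staff who know the arm could also let fluid timing differ without any instruction to do so. In either case the planned data would not reveal it: the form has no bolus times, and the only chart review covers a subset of patients for a different purpose. Bolus times may exist in the medical record, but the plan does not collect them.

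**Working it through.** **1. What the text fixes for each arm**

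| | Arm 1 | Arm 2 |
|---|---|---|
| Volume | 1 L LR | 1 L LR |
| Fluid timing, Study Design | Before the epidural, or unstated, depending on the reading | During and after the epidural |
| Fluid timing, envelope labels | Not given | Not given |
| Fluid timing, Intervention section | Not mentioned | Not mentioned (standard care) |
| Fluid timing on the form | Not collected | Not collected |

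Under the first reading the planned contrast is SCDs plus preload against co-load. Under the second, Arm 1 has no fluid time to compare with Arm 2. No section says the timing is common to both arms.

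**2. The plan's own figure**

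The sample size is not in dispute; it supplies the control rate used below. Inputs from Sample Size Determination: p₁ = 0.0323, p₂ = 0.233, power 0.80, α = 0.05 (two-sided assumed, since sidedness is not stated). With p̄ = (0.0323 + 0.233)/2 = 0.13265,

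n per arm = [1.960·√(2p̄(1−p̄)) + 0.8416·√(p₁(1−p₁) + p₂(1−p₂))]² / (p₂ − p₁)² = 43.6, rounded up to 44.

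This reproduces the stated 44 per group and 88 in total. The approximate power at the planned 60 per arm is 91.0%.

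**3. How far fluid timing alone could move the result**

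The documents give no fluid-timing effect, so the Arm 1 rates below are assumptions. Suppose the SCDs do nothing, Arm 2 has hypotension in 23.3%, and timing alone sets the Arm 1 rate p. With X ~ Bin(60, p) and Y ~ Bin(60, 0.233) independent,

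P(significant) = Σ P(X = x)·P(Y = y), summed over all (x, y) for which the chi-square statistic exceeds 3.841.

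The plan does not say whether a continuity correction applies, so both versions are shown.

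| Assumed Arm 1 rate | Relative risk (p/0.233) | Uncorrected | Continuity-corrected |
|---|---|---|---|
| 23.3% (no timing effect) | 1.00 | 5.2% | 2.9% |
| 20% | 0.86 | 7.3% | 4.4% |
| 15% | 0.64 | 20.9% | 14.8% |
| 12% | 0.52 | 36.4% | 28.2% |
| 10% | 0.43 | 49.7% | 40.7% |
| 8% | 0.34 | 64.4% | 55.5% |

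Each entry is the chance of a significant difference between arms when the SCDs have no effect.

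**The case against.** The text leans towards a bolus common to both arms. In the Arm 1 sentence the timing phrase follows the SCDs and runs on to their removal, so it most naturally describes the device. The Intervention section ties the 15 minutes to the SCDs alone, the title speaks of placing SCDs before the epidural, and the envelope labels present the fluid as background to both arms. On that reading the fault is a fluid time that was never written down. The harm is also doubly conditional: timing must differ by arm, and timing must affect hypotension. The documents establish neither. The larger figures in the table need timing alone to cut the rate by about half to two thirds. Finally, drift in co-interventions is possible in any open-label trial, and nothing shows that it happened here.

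Most of this stands. The intended design may well have been a common bolus, the confounding must be stated conditionally, and the table cannot set the severity. The objection does not remove the gap itself. The arm definitions, the only text on fluid timing, time the litre explicitly for one arm and in different words from the other. Staff following them could give two different regimens, and the planned data could neither detect this nor confirm that timing was equal.

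**Conclusion.** The concern holds as a conditional one and should be fixed. It is certain from the text that bolus timing is stated for Arm 2, ambiguous for Arm 1 and not collected in either. Whether timing differs in practice is not known. If it does, the Hypothesis 1 comparison estimates the SCDs together with a fluid timing, and neither randomization nor the unadjusted chi-square test can separate them.

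The size cannot be derived from the documents. Under the assumptions stated (inert SCDs, 23.3% in Arm 2, 60 per arm), the distortion is small for a mild timing effect and large for a strong one. Confidence is medium: the drafting and data gaps are plain, but the wording elsewhere favours a common bolus.

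**What to change.** - **Arm definitions.** Amend Study Design so that the 1 L LR bolus has one identical stated timing relative to the epidural in both arms. Which timing is the clinical team's choice. Align the envelope labels and the Intervention section with it.
- **Data form.** Replace the yes/no fluid item with start time, stop time and volume, in both arms.
- **Patients already treated, if any.** The planned start (2.25.2021) precedes the date of this version (December 27, 2022), so some may exist, although the document does not report enrolment. For them, take bolus times from the chart where recorded and report them by arm.
- **Reporting.** If timing proves to have differed by arm, state the conclusion as being about SCDs plus that fluid timing, not SCDs alone.

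The cost is a short protocol amendment, nurse re-education, a few form fields and a chart look-up for anyone already treated. The sample size does not change.

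### The arm is revealed right after consent, while the tracing criteria stay open until the epidural, and the plan has no re-check and no rule for women who fail afterwards

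*Combined protocol and SAP*

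**What the plan says.** The document is a combined protocol and SAP.

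- **Approach (Data Collection).** "When a patient who meets the inclusion/exclusion criteria is admitted, a nurse will describe the study". Informed consent, under Ethical Considerations, likewise has the criteria met before the consent form is signed.
- **Randomisation (Data Collection).** "After the patient provides written informed consent, the nurse will remove the next envelope out of a box of prefilled and sealed opaque envelopes". Inside are the subject number and "the study Arm that the patient has been randomized to, either" SCD plus fluid bolus or fluid bolus alone. No step is described between consent and the draw.
- **Criteria that look ahead (Participants).** Inclusion requires "Will receive epidural analgesia" and "Category 1 tracings only before epidural placement". Exclusion lists "Fetal heart rate abnormalities before epidural".
- **Design and timing (Study Design).** "This study will use a randomized, non-blinded, controlled design with two arms". Arm 1 patients "have SCDs applied 15 minutes before epidural placement and will be removed 1 hour after epidural placement".
- **Removal from analysis (Sample Size Determination).** Missing data is the only ground named.
- **Analysis (Statistical Analysis).** Both chi-square comparisons are defined by whether patients used the device, not by assigned arm. No intention-to-treat set is defined.

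**The concern.** Eligibility should be settled before the arm is known. Here the tracing criteria are still running when the envelope is opened, so a woman with a Category 1 tracing at consent can be allocated and then show an abnormality before her epidural. Another can be allocated and then receive no epidural, so that she has no one-hour window in which the outcomes are observed. The plan does not say what happens to either.

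Each way of filling that gap has a cost:

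- **Dropping women.** The analysed groups are no longer the randomised groups. The decision would rest on the fetal tracing, which is tied to the Hypothesis 2 outcome and to one of the two interim stopping triggers, and it would be made by unblinded staff.
- **Keeping women with no epidural.** They cannot have post-epidural hypotension, so they dilute Hypothesis 1.

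There is also an asymmetry. In Arm 1 the last 15 minutes of the eligibility window fall while the SCDs are on; in Arm 2 they do not. The same criterion is judged partly on treatment in one arm and entirely off it in the other.

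**Working it through.** **1. Does the timing conflict depend on how long after admission the epidural is given?** No. Arm 1 has SCDs on 15 minutes before placement, so the arm must be known at least that early. Both tracing criteria run to the epidural itself. Even if the envelope were opened at the last workable moment, about 15 minutes of the eligibility window would remain. Opening it after consent at admission can only lengthen that.

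**2. Does anything else in the document close the gap?** There is no re-check between consent and the draw, and no rule for a changed tracing or an epidural not given. The data collection form records the time of epidural placement but has no field for the tracing before it. The blinded raters review only charts flagged for a fetal heart rate intervention.

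**3. The plan's own sample size.** Inputs from Sample Size Determination: p1 = 0.233, p2 = 0.0323, power 0.80, α = 0.05 (taken as two-sided). The mean rate is 0.13265 and d = 0.2007.

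n = [1.960·√(2·0.13265·0.86735) + 0.842·√(0.233·0.767 + 0.0323·0.9677)]² / 0.2007² = 43.6, rounded up to 44 per group.

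The stated 44 per group (88 in total) reproduces, so this is a design point and not an arithmetic error. The margin is (120 − 88)/120 = 26.7%. At 60 per group, power is 91.0%.

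**4. Dilution if women with no epidural are kept as non-events.** The documents give no rate, so q is an assumption, taken as equal in both arms. Both event rates are multiplied by (1 − q). Power = Φ[(d − 1.960·SE₀)/SE₁], where SE₀ uses the pooled rate, SE₁ uses the separate rates, and n = 60 per arm.

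| q | No SCD | SCD | Difference (points) | Power |
|---|---|---|---|---|
| 0 | 23.3% | 3.23% | 20.1 | 91.0% |
| 10% | 21.0% | 2.9% | 18.1 | 87.2% |
| 20% | 18.6% | 2.6% | 16.1 | 82.3% |
| 30% | 16.3% | 2.3% | 14.0 | 76.2% |

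**5. Selective exclusion, as an illustration only.** Every input here is assumed. Suppose there is no true effect, 20% of women have an equivocal tracing before the epidural, and the later Category 2 risk is 60% for them and 25% for the rest. If a fraction x of the equivocal women is excluded, the observed rate is [0.20(1 − x)·0.60 + 0.80·0.25] / [0.20(1 − x) + 0.80].

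- x = 0.75 in Arm 1 and 0.25 in Arm 2: 27.1% vs 30.5%, a spurious 3.5 points. With 51 vs 57 women, the exact rejection rate of the uncorrected two-sided chi-square test is 6.8%.
- x = 1 in Arm 1 and 0 in Arm 2: 25.0% vs 32.0%, or 7 points. With 48 vs 60 women, the rejection rate is 13.1%.
- No exclusions (60 vs 60 at 32%): the rejection rate is 5.2%.

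**The case against.** The strongest reply is that the protocol describes no exclusion after randomisation. It says criteria are met before the approach and before consent. A reader might infer that eligibility is actually decided later by staff who know the arm, but the documents do not support that: it is not a stated procedure, only something the plan leaves open. This part of the reply stands.

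Several other limits also stand:

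- The epidural criterion can be read as intention at consent, and the two tracing criteria overlap. In substance, one tracing criterion carries the point.
- The text ties the approach to admission but gives no interval. The only documented minimum gap is about 15 minutes, so high failure rates have no support.
- A reader might infer that women who fail later use up places in the 120. The text does not say so: Participants speaks of enrolling 120 women who meet the criteria, which could be read as not counting them.
- A reader might also infer that later exclusions could never be verified. They could, because tracings are in the medical record and the epidural time is on the form. The plan simply schedules no such review.
- Sealed opaque envelopes protect concealment up to the draw. The risk lies after it.
- Diluted power stays above the planned 80% at an assumed 20%, and dilution acts toward no effect. Nothing in the documents suggests that exclusion rates would differ between arms as in step 5.

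None of this removes the conflict. Under any reading, the tracing criteria are still open when the arm is revealed.

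**Conclusion.** The point holds as a conflict between the moment of randomisation and the wording of the criteria, made worse by the lack of any rule for later failures and by an analysis defined by device use. It leaves open exclusions made with the arm known, on a variable tied to the Hypothesis 2 outcome; if women with no epidural are kept instead, Hypothesis 1 is diluted.

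The size is not known, because no rate is documented. On assumed no-epidural rates of 10% to 30%, power at 60 per arm would be about 87% to 76% instead of 91%. Spare enrolment can absorb that loss of power within limits, but it would not remove bias from selective exclusion. The figures in step 5 show only that the bias could be modest or material, depending on inputs that nobody has. The case for acting rests on the timing conflict and the low cost of the repair, not on a predicted magnitude.

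**What to change.** 1. Keep consent at admission. In Data Collection, state that the envelope stays sealed until the patient requests her epidural, and is opened before the SCD period would begin and only after the nurse has re-confirmed every criterion.
2. Reword both tracing criteria so that they apply up to randomisation. The checkpoint is then the same in both arms and precedes any SCD use.
3. State that consented women who are never randomised do not count toward the 120.
4. In Statistical Analysis, define the primary comparison as all randomised women by assigned arm. A tracing change after randomisation does not remove a woman. The few who are randomised and then receive no epidural stay in their arm and are reported by arm.

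The cost is a short amendment and revised nurse instructions, with no change to treatment and no extra visits. There are two small downsides: more women must be consented to randomise 120, and the envelope is opened at a busier time, with leg measurement and boot sizing to follow before the SCD period.
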